### Study Protocol

**Title:** Risk of Aspergillus infection in patients with chronic structural lung disease

**Objective:** Identify the risk factors associated with fungal infections and investigate acute exacerbation in these patients.

**Background:** More attention has been paid to improving the quality of life and long-term management of patients with structural lung diseases such as chronic obstructive pulmonary disease (COPD) and bronchiectasis, whose repeated acute exacerbations lead to greater dependence on systemic and inhaled glucocorticoids. At the same time, the incidence of aspergillus pneumonia also increased.

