#### Methodology:

- **Study Design:** The risk factors of aspergillus pneumonia were compared between aspergillus colonization group and aspergillus pneumonia group.
- **Participants:** Patients with chronic lung disease were identified as positive for Aspergillus fumigatus through sputum microscopy. According to diagnostic criteria, patients diagnosed with IPA and CPA and were assigned to the Aspergillosis pneumonia group, while the remaining patients were included in the Aspergillus colonization group. Then, Risk factors for aspergillus pneumonia, invasive pulmonary aspergillus disease, and chronic pulmonary aspergillus disease, such as the use of high-dose corticosteroids, inhaled corticosteroids, and the extent of damage to basic lung structures, were identified by comparing the aspergillus colonization group with the aspergillus infection group.
- **Procedures:**

- Patients diagnosed with chronic lung disease were screened out who were qualified by sputum microscopy and positive for aspergillus in sputum culture.
- The chest high-resolution computed tomography (HRCT), serum Aspergillus specific IgG antibody, serum aspergillus IgM antibody and serum GM test were performed.
- The risk factors of aspergillus infection group and aspergillus colonization group were compared.
- **Ethics Approval:** Granted by the Medical Ethics Committee of Sichuan Provincial People's Hospital.

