### **Statistical Analysis Plan**

#### **Data Analysis Strategy:**

1. **Descriptive Statistics:**
  - Summarize participant characteristics using means and standard deviations for continuous variables and frequencies for categorical variables.
2. **Identify independent risk factors:**
  - Independent risk factors for aspergillus infection were determined by multivariate logistic regression analysis.
3. **Comparison Between Groups:**
  - The area under ROC curve (AUC) was used to evaluate the classification effect of the binary classification model among Aspergillus pneumonia group, IPA group and CPA group.
4. **Threshold Analysis:**
  - Specific cut-off values for Aspergillus specific IgG antibody  $\times$  lung structural injury image score was determined to maximize diagnostic accuracy, focusing on sensitivity, specificity, and Youden index.

**Software:** Statistical analysis will be conducted using SPSS version 25.0 or a similar statistical package.

**Ethical Considerations:** Data will be anonymized to protect patient confidentiality, with all procedures carried out in accordance with the Declaration of Helsinki.

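### Does the acute-exacerbation clause in the Objective need its own definition and analysis in the plan?

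*Combined protocol and SAP*

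**What the plan says.** The Objective joins two aims in one sentence: "Identify the risk factors associated with fungal infections and investigate acute exacerbation in these patients". The Background then describes patients with structural lung disease "whose repeated acute exacerbations lead to greater dependence on systemic and inhaled glucocorticoids". These are the only two references to exacerbation in the available text.

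The rest of the plan is about Aspergillus. Study Design says "The risk factors of aspergillus pneumonia were compared between aspergillus colonization group and aspergillus pneumonia group", and the third Procedures bullet repeats the contrast: "The risk factors of aspergillus infection group and aspergillus colonization group were compared". Under Participants, the candidate risk factors are given as examples, "such as the use of high-dose corticosteroids, inhaled corticosteroids, and the extent of damage to basic lung structures".

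In the Statistical Analysis Plan, item 1 is a general summary of patient characteristics that names no variable. Item 2 states "Independent risk factors for aspergillus infection were determined by multivariate logistic regression analysis". Item 3 assesses the "classification effect of the binary classification model among Aspergillus pneumonia group, IPA group and CPA group". Item 4 seeks "Specific cut-off values for Aspergillus specific IgG antibody" combined with the imaging score.

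**The concern.** A stated objective should be traceable to a variable, a time window and an analysis, and the exacerbation clause leads to none of them. It is not even clear what kind of quantity is meant. Exacerbation could be a history that precedes Aspergillus disease, an event that follows it, or the clinical setting in which these patients are seen. Each reading would need different data and a different analysis.

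Two things could be at stake. The clause might never be reported, or its definition and window might be chosen after the data are seen. There is also a possible bias if exacerbation is used as a risk factor without a cut-off at the index sputum. An episode that is itself the onset of Aspergillus pneumonia could then be counted as a preceding exacerbation, so that a consequence of disease would look like a cause.

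**Working it through.** The plan states no figure on this point, so there is nothing to reproduce or recompute. The check is a reading of the sections side by side.

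**Where exacerbation appears.** Objective: 1. Background: 1. Methodology: 0. Statistical Analysis Plan: 0. The total is 1 + 1 + 0 + 0 = 2. None of the four SAP items names it.

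**What each reading of the clause would need, and what the plan already offers.**

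| Reading | Needs | Already available |
|---|---|---|
| Prior history, as a risk factor | A covariate in a model of infection | Item 2 supplies the model and fixes no covariate list; the list under Participants is illustrative |
| Descriptive characteristic or setting | A summary by group | Item 1 supplies it |
| Later outcome | Follow-up and an outcome analysis | Neither is described |

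So two of the three readings can be met without altering the plan. The third would require a follow-up component that nothing in the design suggests.

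**Does absence from Procedures show that the variable was not collected?** No. Corticosteroid use is an explicitly named risk factor, and it does not appear among the Procedures either. That list covers sputum screening, imaging and serology. It is not an inventory of the data.

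**Does the gap alter any stated analysis?** The grouping depends on the diagnostic criteria for invasive and chronic aspergillosis. The dependent variable in item 2 is infection. Items 3 and 4 concern classification and a cut-off for Aspergillus disease. None takes exacerbation as a required input, so none gives a different answer because the clause is undeveloped.

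**How firm is the bias argument?** It needs two conditions. Exacerbation must be treated as a risk factor, and the sputum must have been taken because the patient was getting worse. The documents do not choose the first reading, and they do not say why or when sputum was obtained.

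**Would writing exacerbation history into item 2 be a clear gain?** Not clearly, for three reasons:

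- It would settle the three-way ambiguity in favour of one reading and would drop an outcome aim if that is what was meant.
- The Background places exacerbations upstream of glucocorticoid use. In a model that also contains steroid terms, the exacerbation coefficient would omit whatever acts through steroids, and a null result could be misread.
- The Methodology and SAP items 2 to 4 are written in the past tense, although the Software and Ethical Considerations lines use the future. If the data are already in hand, rewording the Objective would itself be a post hoc change.

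**The case for a change.** The strongest case for a change is that permitting a variable is not the same as planning it. The clause uses the language of an aim. The plan finds room for lesser matters, such as the Youden index and the software version, so brevity alone does not excuse silence on a stated objective. The main text of the Methodology and SAP is available, and neither contains a visible redaction that could hide the missing detail. The repair also looks small: one variable, one model term and one reworded sentence.

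The factual part of this stands. The plan does not guarantee that the clause will be addressed, and the choice of role and window is left open.

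The rest is weaker. Exacerbation is not singled out: item 2 lists no covariates at all, and the corticosteroid dose category and the diagnostic criteria are also left undefined in this short document. The claim of small cost assumes dated exacerbation records, which the documents do not mention, and a sample large enough to carry another term, which cannot be judged because no sample size is given.

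**Conclusion.** The observation is accurate, but it is a low-severity gap in detail that does not require a change to the plan. No stated rule or figure is shown to give a wrong result, and the comparison of infection with colonisation stands whatever is done with the clause. The residual risk is confined to half a sentence of the Objective, which may go unreported or be defined late. It cannot be quantified from the documents.

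This conclusion assumes that exacerbation is meant as history or as a descriptive feature, which fits a design with no described follow-up. On that basis an experienced analyst would fill the gap sensibly: say which role was taken, count only episodes before the index sputum if it is an exposure, look at the estimate with and without the steroid terms, and label the result exploratory if it was defined after data access. If the investigators intended exacerbation as a later outcome, the plan does not deliver that aim, but its Aspergillus analyses would still be unaffected.

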#### Methodology:

- **Study Design:** The risk factors of aspergillus pneumonia were compared between aspergillus colonization group and aspergillus pneumonia group.
- **Participants:** Patients with chronic lung disease were identified as positive for Aspergillus fumigatus through sputum microscopy. According to diagnostic criteria, patients diagnosed with IPA and CPA and were assigned to the Aspergillosis pneumonia group, while the remaining patients were included in the Aspergillus colonization group. Then, Risk factors for aspergillus pneumonia, invasive pulmonary aspergillus disease, and chronic pulmonary aspergillus disease, such as the use of high-dose corticosteroids, inhaled corticosteroids, and the extent of damage to basic lung structures, were identified by comparing the aspergillus colonization group with the aspergillus infection group.
- **Procedures:**

- Patients diagnosed with chronic lung disease were screened out who were qualified by sputum microscopy and positive for aspergillus in sputum culture.
- The chest high-resolution computed tomography (HRCT), serum Aspergillus specific IgG antibody, serum aspergillus IgM antibody and serum GM test were performed.
- The risk factors of aspergillus infection group and aspergillus colonization group were compared.
- **Ethics Approval:** Granted by the Medical Ethics Committee of Sichuan Provincial People's Hospital.

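### Steroid use and structural damage are analysed as risk factors without any rule that they precede disease, so reverse causation cannot be excluded

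*Combined protocol and SAP*

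**What the plan says.** The Participants item of the protocol's Methodology names the candidate factors as "such as the use of high-dose corticosteroids, inhaled corticosteroids, and the extent of damage to basic lung structures". It says that they "were identified by comparing the aspergillus colonization group with the aspergillus infection group". Group membership rests on diagnosis: "patients diagnosed with IPA and CPA and were assigned to the Aspergillosis pneumonia group", and everyone else forms the colonization group. No date of onset or diagnosis is defined.

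The Procedures first screen for patients with chronic lung disease who are "positive for aspergillus in sputum culture". The next step reads: "The chest high-resolution computed tomography (HRCT), serum Aspergillus specific IgG antibody, serum aspergillus IgM antibody and serum GM test were performed". No scan from before the positive sputum is asked for.

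The SAP's Data Analysis Strategy adds only this: "Independent risk factors for aspergillus infection were determined by multivariate logistic regression analysis". It gives no covariate timing, look-back window or lag. Its Threshold Analysis item seeks a cut-off for IgG multiplied by an image score ("lung structural injury image score was determined to maximize diagnostic accuracy"), so a structural score also appears there as a marker of present disease.

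The Background describes patients with structural lung disease "whose repeated acute exacerbations lead to greater dependence on systemic and inhaled glucocorticoids".

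**The concern.** To call something a risk factor is to say that it came before the disease. Here both named kinds of factor can also be consequences of it.

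- **Steroids.** The Background ties steroid use to exacerbations. If early aspergillosis is treated as an exacerbation, the disease itself produces the exposure.
- **Structural damage.** If the damage score is read from the HRCT done after the positive sputum, lesions caused by Aspergillus can raise it.

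Covariates in the logistic model do not solve this. The fault lies in when the exposure was recorded, and adjusting for other variables cannot separate exposure before onset from exposure after it. Finding risk factors is the protocol's stated objective and these are the only candidates it names, so the interpretation of the main result is at stake.

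**Working it through.** **What the documents supply.** They give no sample size, exposure rate or effect size, so there is no planned figure to reproduce. The first check is whether any timing rule exists.

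| Item needed for time order | Protocol | SAP |
|---|---|---|
| Onset or index date | none | none |
| Steroid look-back window or lag | none | none |
| Scan from before infection | none; HRCT is listed after screening | none |
| Exclusion of exposure or damage after onset | none | none |

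**Steroids: illustration under assumed inputs.** None of these values comes from the documents.

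- True odds ratio 1.0, so both groups have the same prior exposure, p = 0.20.
- A fraction f of unexposed cases (pneumonia group) starts steroids for symptoms and is counted as exposed: f = 0.05, 0.10 or 0.20.
- A fraction g of unexposed controls (colonization group) does the same: g = 0 or 0.10.

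Counted exposure is p + (1 − p)f in cases and p + (1 − p)g in controls. The observed odds ratio is the ratio of the two odds.

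- Cases: 0.20 + 0.80 × 0.05 = 0.24; 0.20 + 0.80 × 0.10 = 0.28; 0.20 + 0.80 × 0.20 = 0.36. Odds: 0.24/0.76 = 0.316; 0.28/0.72 = 0.389; 0.36/0.64 = 0.5625.
- Controls, g = 0: exposure 0.20, odds 0.20/0.80 = 0.25.
- Controls, g = 0.10: exposure 0.28, odds 0.28/0.72 = 0.389.

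| f in cases | Observed OR, g = 0 | Observed OR, g = 0.10 |
|---|---|---|
| 0.05 | 0.316/0.25 = 1.26 | 0.316/0.389 = 0.81 |
| 0.10 | 0.389/0.25 = 1.56 | 0.389/0.389 = 1.00 |
| 0.20 | 0.5625/0.25 = 2.25 | 0.5625/0.389 = 1.45 |

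In an intermediate case, f = 0.10 and g = 0.05, the odds ratio is 0.389/0.316 = 1.23. In this model the result exceeds 1 when f > g, equals 1 when f = g, and falls below 1 when f < g.

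Prior exposure matters too. With g = 0 and f from 0.05 to 0.20, the range is 1.18 to 1.83 at p = 0.30 and 1.11 to 1.50 at p = 0.50.

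**Structural damage: no arithmetic is possible.** The documents give no score distribution. The argument rests on order: screening for Aspergillus comes first, HRCT second, and no other imaging is listed. A plan that measures damage only after the organism is found cannot show that the damage came first.

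**The case against.** The strongest counter-argument concerns the controls. A reader might infer that the error acts in the pneumonia group only and so always inflates the odds ratios. The documents do not support that. The Background links exacerbations to steroids in structural lung disease generally, and colonized patients come from the same population and enter through the same positive sputum. They too can be given steroids for worsening symptoms. With equal rates in the two groups the steroid bias in the illustration vanishes, and with a higher rate in controls it reverses. A higher rate in cases is plausible, since only they have symptoms caused by aspergillosis, but it is not shown.

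A second tempting inference is that exposure after onset *is* being counted. The text shows only that nothing excludes it.

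On structural damage, the phrase about basic lung structures may mean underlying, pre-existing disease, and the protocol does not say outright that the risk-factor score comes from the listed HRCT. That is a fair reading of intent. However, no listed procedure measures damage before infection, so the intent cannot be carried out as written. Nor do the documents say that the damage score and the Threshold Analysis score are the same measure.

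Finally, a look-back that ends on the day of the first positive sputum does not cure the problem. Steroids given for early aspergillosis before that sample would still fall inside the window. This stands, and it shapes the remedy.

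**Conclusion.** The point holds in this form: the plan does not define when steroid exposure and structural damage are measured relative to disease, so reverse causation cannot be excluded for either. Both the size and the direction of the steroid bias are unknown. Under the stated assumptions, a true odds ratio of 1.0 could appear as anything from 0.81 to 2.25, depending on how often each group starts steroids for symptoms. The size of the structural bias cannot be estimated from the documents. The plan should be changed on this point, because the alternative is a risk-factor claim that its data cannot support. The documents do not, however, show that the odds ratios will be inflated.

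**What to change.** Add a timing rule to the SAP:

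1. **Index date.** Use the date of the first positive sputum in both groups. Every participant has one by the entry criterion.
2. **Steroid exposure.** Make the primary measure a fixed look-back that ends a set lag before the index date, with both lengths fixed before analysis (for example a 90-day window and a 14-day lag). Add sensitivity analyses with no lag and with a longer lag. The longer lag matters particularly for chronic pulmonary aspergillosis, where 14 days cannot be assumed to reach back before onset.
3. **Structural damage.** Score it on the last scan before the index date where one exists. Otherwise report the score as an associated or diagnostic feature, not as a risk factor.
4. **Limitation.** State that these rules reduce reverse causation but do not remove it, because disease may begin well before the first positive sample.

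The change needs no new patients, tests or change in care. It does need dated prescriptions and earlier scans. The documents do not state the data source, so availability is unknown. Some patients will lack one or the other, and the number missing should be reported by group. If dates prove unobtainable, the fallback is to report associated factors throughout instead of risk factors, which costs only wording.

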### **Statistical Analysis Plan**

#### **Data Analysis Strategy:**

1. **Descriptive Statistics:**
  - Summarize participant characteristics using means and standard deviations for continuous variables and frequencies for categorical variables.
2. **Identify independent risk factors:**
  - Independent risk factors for aspergillus infection were determined by multivariate logistic regression analysis.
3. **Comparison Between Groups:**
  - The area under ROC curve (AUC) was used to evaluate the classification effect of the binary classification model among Aspergillus pneumonia group, IPA group and CPA group.
4. **Threshold Analysis:**
  - Specific cut-off values for Aspergillus specific IgG antibody  $\times$  lung structural injury image score was determined to maximize diagnostic accuracy, focusing on sensitivity, specificity, and Youden index.

**Software:** Statistical analysis will be conducted using SPSS version 25.0 or a similar statistical package.

**Ethical Considerations:** Data will be anonymized to protect patient confidentiality, with all procedures carried out in accordance with the Declaration of Helsinki.

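### The only stated risk-factor comparison pools IPA and CPA, so it cannot attribute a factor to either subtype, although the protocol seeks risk factors for both

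*Combined protocol and SAP*

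**What the plan says.** **Groups.** Under Methodology, Participants, "patients diagnosed with IPA and CPA and were assigned to the Aspergillosis pneumonia group", "while the remaining patients were included in the Aspergillus colonization group". The case group is therefore IPA and CPA together, and colonization is everyone else.

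**Targets and method.** The same paragraph names three targets, "Risk factors for aspergillus pneumonia, invasive pulmonary aspergillus disease, and chronic pulmonary aspergillus disease", and one method for all of them: they "were identified by comparing the aspergillus colonization group with the aspergillus infection group". Study Design states the same two-group contrast: "The risk factors of aspergillus pneumonia were compared between aspergillus colonization group and aspergillus pneumonia group". The last step under Procedures repeats it. The Objective is also about infection overall: "Identify the risk factors associated with fungal infections".

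**Analysis.** SAP item 2 is the only stated risk-factor model: "Independent risk factors for aspergillus infection were determined by multivariate logistic regression analysis". It names no IPA or CPA outcome. SAP item 3 applies the AUC to a "binary classification model among Aspergillus pneumonia group, IPA group and CPA group" without saying what each group is compared with. SAP item 4 derives a cut-off for the product of IgG and image score without naming the outcome being classified.

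**The concern.** One sentence promises answers for three outcomes and supplies a contrast for one. An odds ratio comparing colonized patients with IPA and CPA cases combined reflects a mixture of the two subtype effects, and the mixture depends on how many cases are of each type. If a candidate factor such as corticosteroid use or structural lung damage acted mainly on one subtype, the pooled estimate would be pulled toward the weaker effect. It could then be missed, or be reported as a risk factor for both diseases. Followed literally, the plan leaves two of the three questions unanswered or answers them with an estimate that cannot distinguish them.

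**Working it through.** The documents give no sample size, subtype split, exposure rate, effect size or AUC, so there is no figure of the plan's own to reproduce. The first check is textual; the rest is illustration.

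**1. Question against stated contrast**

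| Question | Where asked | Stated contrast | Answered by item 2 as written? |
|---|---|---|---|
| Pneumonia (IPA and CPA combined) | Objective, Study Design, Participants | Colonization vs infection | Yes |
| IPA | Participants | The same pooled contrast | No |
| CPA | Participants | The same pooled contrast | No |

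**2. What pooling can do to an odds ratio.** All inputs are assumed: one binary exposure, no adjustment (item 2 is multivariable), exposure p0 = 0.30 in colonization, and IPA share of cases f = 0.25, 0.50 or 0.75.

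- Exposure in subtype k: p_k = OR_k × odds(p0) / (1 + OR_k × odds(p0)). With odds(0.30) = 0.4286, this is 0.632 for OR 4, 0.462 for OR 2, 0.391 for OR 1.5 and 0.300 for OR 1.
- Pooled exposure: p = f × p_IPA + (1 − f) × p_CPA. Pooled OR = odds(p) / odds(p0).
- Worked case, IPA OR 4, CPA OR 1, f = 0.50: p = 0.5 × 0.632 + 0.5 × 0.300 = 0.466; odds = 0.872; pooled OR = 0.872 / 0.4286 = 2.03.

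| IPA OR / CPA OR | p0 | f = 0.25 | f = 0.50 | f = 0.75 |
|---|---|---|---|---|
| 4 / 1 | 0.30 | 1.45 | 2.03 | 2.84 |
| 4 / 1 | 0.20 | 1.52 | 2.15 | 2.96 |
| 4 / 1 | 0.50 | 1.35 | 1.86 | 2.64 |
| 4 / 1.5 | 0.30 | 1.92 | 2.44 | 3.11 |
| 2 / 1 | 0.30 | 1.20 | 1.43 | 1.70 |
| 2 / 2 | 0.30 | 2.00 | 2.00 | 2.00 |

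A CPA odds ratio of 1 is the harsher case. With 1.5 the dilution is smaller, and with equal odds ratios there is none.

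**3. Power and precision.** Further assumptions: 100 cases, 100 colonized, p0 = 0.30, two-sided 5%. SE(log OR) = sqrt[1/(n1 p1(1 − p1)) + 1/(n0 p0(1 − p0))], with n1 = 100 for the pooled model and 100f for IPA alone. Wald power = Φ(|log OR|/SE − 1.96).

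| IPA OR / CPA OR | Pooled power (f = 0.25 / 0.50 / 0.75) | IPA-only power | SE ratio, IPA-only to pooled |
|---|---|---|---|
| 4 / 1 | 23 / 67 / 94% | 84 / 97 / 99% | 1.56 / 1.23 / 1.09 |
| 2 / 1 | 9 / 22 / 43% | 33 / 49 / 59% | 1.50 / 1.19 / 1.07 |
| 2 / 2 | 65 / 65 / 65% | 33 / 49 / 59% | 1.54 / 1.21 / 1.07 |

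A subtype model can find what the pooled one misses when effects differ. When effects are equal the pooled model is stronger, and at an odds ratio of 2 the subtype model is underpowered at every share shown.

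**4. Item 3, negative class (minor).** Assume a normal marker with SD 1, mean 0 in colonization, 1 in IPA and d in CPA, with 100 colonized patients. With CPA excluded, the IPA AUC is Φ(1/√2) = 0.760. With CPA counted as negative it is (1 − w)Φ(1/√2) + wΦ((1 − d)/√2), where w is the CPA share of the negatives.

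| CPA patients | d = 0 | d = 0.5 | d = 1 | d = 1.5 |
|---|---|---|---|---|
| 50 (w = 50/150) | 0.760 | 0.720 | 0.673 | 0.627 |
| 10 (w = 10/110) | 0.760 | 0.749 | 0.737 | 0.724 |

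The two conventions answer different questions. The gap is small when the other subtype is rare or resembles colonization.

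**The case against.** The best defence is that subtype models are already implied. Item 3 evaluates a binary model for pneumonia, IPA and CPA, the only model the SAP names is the logistic regression in item 2, and the Participants paragraph lists the same three outcomes. On that reading, infection in item 2 is an umbrella term for three regressions. This is plausible, and it means the defect may be one of wording rather than intent. It does not settle the matter: the model in item 3 could equally be the IgG-by-image-score product of item 4, and the Participants paragraph expressly gives the pooled comparison as the method. An implied model still has no stated outcome or reference group.

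It is also fair that the Objective, Study Design and Procedures all ask the pooled question, which item 2 answers, and that the protocol lists the same candidate factors for all three outcomes with no sign that their effects differ. Both points stand. They limit the weight of the finding, but the subtype question is still on the page without a stated analysis.

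A reader might go further and infer that the pooled regression is wrong, or that the item 3 AUCs have no reference group at all. The documents support neither. The pooled contrast is valid for pneumonia. Colonization is the natural negative class in item 3 because it is defined as the remaining patients, and for the pooled AUC it is the only candidate. What is open is whether the other subtype is excluded or counted as negative in the IPA and CPA curves, which is missing detail rather than an error.

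**Conclusion.** The point holds for the risk-factor analysis and should be fixed. As written, the plan cannot support a conclusion that a factor raises the risk of IPA or of CPA specifically; it can support one about pneumonia against colonization. The textual part needs no assumption beyond taking item 2 as written. The numbers rest wholly on assumed inputs and an unadjusted single-exposure model. They show that a subtype odds ratio of 4 could appear as anything from about 1.4 to 3.1 across the unequal-effect cases tried, and would be undistorted if the subtypes shared the same effect. That is a possible size, not an expected one, and should not be read as an estimate of bias in this study. The unstated contrasts in items 3 and 4 are a minor clarification.

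**What to change.** Keep the pooled pneumonia-versus-colonization regression. Then take one of two routes.

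**A. Add the subtype analyses.** Extend SAP item 2 with the same regression for IPA versus colonization (CPA excluded) and for CPA versus colonization (IPA excluded), or with a single multinomial model using colonization as the reference. Report odds ratios with 95% intervals. State the number of IPA and CPA cases, and either limit the covariates to what those counts can bear or use a penalised (Firth) fit. Labelling these analyses exploratory is suggested, given their likely power, but that is the sponsor's choice because the protocol does not rank the three outcomes. If confirmatory claims are wanted, multiplicity needs to be addressed.

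**B. Narrow the claim.** Restrict the Participants sentence to pneumonia versus colonization and draw no subtype-specific risk-factor conclusions.

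Under either route, state for every AUC kept in item 3 that colonization is the negative class and, for IPA or CPA, that the other subtype is excluded. If IPA or CPA against all other patients is wanted, list it as a separate AUC. Name the outcome for the item 4 cut-off.

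**Cost.** Route A needs extra wording and two models (or one multinomial) on data already planned. A penalised fit may need other software, which the SAP allows. The price is wider subtype intervals, with standard errors 1.07 to 1.56 times the pooled ones in the illustration, and low power if subtypes are small or effects moderate. Route B costs one sentence and gives up the subtype risk-factor questions.

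### With an open candidate list and no stated group sizes, the logistic regression in SAP item 2 can inflate odds ratios, most likely for IPA and CPA; fix the terms, use a bias-reduced fit and report every term

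*Combined protocol and SAP*

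**What the plan says.** SAP item 2 (Identify independent risk factors) is a single sentence: "Independent risk factors for aspergillus infection were determined by multivariate logistic regression analysis". It names no estimator, list of terms, selection rule or significance level. The Software line reads "Statistical analysis will be conducted using SPSS version 25.0 or a similar statistical package".

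The outcomes and candidates come from the Methodology, under Participants. Three outcomes are of interest: "Risk factors for aspergillus pneumonia, invasive pulmonary aspergillus disease, and chronic pulmonary aspergillus disease". The candidates are introduced as examples, "such as the use of high-dose corticosteroids, inhaled corticosteroids, and the extent of damage to basic lung structures", so three are named but the list is open. On the groups, "patients diagnosed with IPA and CPA and were assigned to the Aspergillosis pneumonia group", while "the remaining patients were included in the Aspergillus colonization group". IPA and CPA are therefore subsets of the case group, and neither can have more cases than the pneumonia group as a whole.

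No sample size or group size is given for any comparison.

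**The concern.** ML log odds ratios are biased away from zero when the smaller outcome group is small relative to the number of coefficients. Nothing in the plan limits that ratio. It is likely to be lowest for IPA and CPA, where the cases are only part of the pneumonia group. Reporting only the factors that reach significance exaggerates the effects further, because in small samples mainly the overestimates cross the threshold.

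Identifying risk factors is the stated objective, so these odds ratios are the main result. At stake are effect sizes that are too large and unstable in the smaller groups.

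**Working it through.** **Inputs.** The plan has no figure to reproduce. Group sizes, number of terms, effect sizes and correlations below are all assumptions. The documents supply only the model type, the three outcomes, the subset relation and the three named factors.

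**Estimators.** ML maximises the log-likelihood l(β). Firth maximises l(β) + ½ log|I(β)|, where I is the information matrix; this removes the leading term of the small-sample bias.

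**Step 1: ten terms, true steroid odds ratio (OR) 2.5.** There were 1,500 data sets per setting, predictor correlation was about 0.3, and ML and Firth used the same ten terms. Ranges show the spread over repeat simulations.

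| Cases/controls | Smaller group per term | Median OR, ML | Median OR, Firth | RMSE of log OR, ML | RMSE of log OR, Firth | Median OR if p<0.05, ML | Median OR if p<0.05, Firth |
|---|---|---|---|---|---|---|---|
| 20/80 | 20/10 = 2 | 2.8–3.1 | 2.4–2.6 | 0.81–0.83 | 0.64–0.66 | 6.1 | 4.9–5.0 |
| 30/90 | 30/10 = 3 | 2.7–2.8 | 2.4–2.5 | 0.63–0.65 | 0.54–0.55 | 4.5 | 4.0 |
| 50/100 | 50/10 = 5 | 2.7–2.8 | 2.5–2.6 | 0.49–0.50 | 0.43–0.44 | 3.6 | 3.3–3.4 |
| 100/150 | 100/10 = 10 | 2.6 | 2.5 | 0.35 | 0.32 | 2.8 | 2.7 |

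**Step 2: when it does not matter.** With three terms only, the ML median OR was 2.54 (20/80), 2.58 (30/90) and 2.45 (50/100). With ten terms and 200 or 300 patients in each group, ML log-OR bias averaged +4% and +2%. With six terms at 20/80, ML gave 2.7 and Firth 2.5.

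**Step 3: IPA and CPA against pneumonia.** These runs used ten terms, correlation 0.2 and true ORs of 2.5, 2.0 and 1.8. Average ML log-OR bias was +11% at 60/90, +15% at 30/90 and +19% at 20/90. If colonization is the smallest group, it was +7% at 200/40 and +12% at 100/40. Monte Carlo error is about 2 percentage points, somewhat more in the 200/40, 100/40 and 200- and 300-per-group runs.

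**Step 4: factors selected by significance.** The share of the excess that Firth removes is (ln OR_ML − ln OR_Firth) / (ln OR_ML − ln 2.5), using the conditional medians in Step 1:

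- 20/80: (ln 6.1 − ln 5.0)/(ln 6.1 − ln 2.5) = 0.199/0.892 = 22%
- 30/90: (ln 4.5 − ln 4.0)/(ln 4.5 − ln 2.5) = 0.118/0.588 = 20%
- 50/100: (ln 3.6 − ln 3.4)/(ln 3.6 − ln 2.5) = 0.057/0.365 = 16%

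Under the Step 3 assumptions, Firth combined with a list shortened to about one term per 10 smaller-group patients (minimum three) removed 28% to 49%.

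**Step 5: shortening the list by dropping adjusters.** When real, correlated covariates were left out of a small-group model, the median OR was 2.85–3.0, against 2.4–2.6 for Firth on the full list. In the Step 3 set-up at 30/90, dropping one real factor gave Firth a bias of +13% (correlation 0.2) or +32% (correlation 0.5), against +14% and +15% for ML on all ten terms.

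**The case against.** The strongest reply is that the size of the problem is assumed. The plan names three factors, and with those alone ML is nearly unbiased and Firth moves the median OR by less than 0.1. On that view the real gap is the missing sample size and term list, and Firth is a matter of taste. This stands in part: the inflation is conditional, and fixing a short list earns some of the gain. It does not dispose of the point. The named factors are only examples, and a claim of independence needs adjustment for more than those three. Where terms are many and cases few, Firth had lower bias and never a higher RMSE.

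Three stronger readings are tempting, and the documents do not support them:

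- A reader might infer that the reported odds ratios will be inflated. With no group sizes or number of terms stated, only *can be* is justified.
- A reader might infer that the plan specifies ML, or IPA and CPA models, in item 2. ML is an inference from unqualified logistic regression and the software named. Item 2 mentions only Aspergillus infection, and the separate outcomes come from the Methodology.
- A reader might infer that a bias-reduced fit on a capped list cures most of the exaggeration. Step 4 shows that for significant factors most of it remains, and Step 5 that a cap which drops adjusters can add bias.

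**Conclusion.** The point holds conditionally. If the smaller group is small relative to the number of terms, as is most likely for IPA and CPA, the analysis on its natural reading can overstate odds ratios. With ten terms and a true OR of 2.5, the ML median is about 3.0 at 20/80 and 2.7–2.8 at 30/90, against about 2.5 with Firth. With three terms, or about 100 or more cases, the difference is negligible.

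These figures rest on assumed sizes, effects and correlations. The simulations used Wald tests, so they do not assess the profile intervals recommended below. The change is worth making because it costs little and alters almost nothing if the groups turn out large. It corrects average small-sample bias; it does not correct selection on significance, which only full reporting addresses.

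**What to change.** Replace the sentence in SAP item 2 with:

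> Models will be fitted by Firth bias-reduced logistic regression with profile penalised-likelihood 95% confidence intervals. The terms (systemic corticosteroids, inhaled corticosteroids, structural damage, age, sex, underlying disease) are fixed before group data are examined and all are kept in each model. All are reported with odds ratios and intervals whatever their p-values, and group sizes are stated. Results for an outcome with fewer than 10 patients per term in the smaller group are labelled exploratory.

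With six terms the exploratory label applies below 6 × 10 = 60 patients in the smaller group. If underlying disease has more than two categories, each extra coefficient should count as a term. Age, sex and underlying disease should not be removed when a group is small (Step 5); the label handles that case.

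**Cost.** SAP wording only, plus a package other than base SPSS, which the Software line allows. Slightly fewer factors will reach nominal significance (38–39% with Firth against 45% with ML at 30/90 in Step 1), and fewer candidates will be examined.
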